3. PARTICIPANT SELECTION

3.1 Inclusion Criteria

1. Diagnosed with clinical or pathologic stage 0-III invasive breast cancer with Tis, TX, or T1-T3 tumor
2. Has been treated with mastectomy
3. Has undergone immediate reconstructive surgery with placement of a tissue expander or permanent implant at time of mastectomy
4. Is a candidate for unilateral post-mastectomy radiation therapy as per local, institutional practice (post-mastectomy radiation therapy is indicated for most patients with positive lymph nodes at time of surgery and infrequently for selected node-negative patients)
5. Use of bolus is permitted, but not required
6. Age ≥ 18

3.2 Exclusion Criteria

1. T4 cancer
2. History of prior ipsilateral breast radiation therapy
3. Uncontrolled intercurrent illness including, but not limited to, ongoing or active infection, symptomatic congestive heart failure, unstable angina pectoris, and/or mental health illness that the consenting investigator feels would affect patient's ability to participate in this study
4. Pregnant or nursing
5. History of a different malignancy except for the following circumstances:
 - Either disease-free for at least five years **OR** deemed by the investigator to be at low risk for recurrence of that malignancy.

- Cervical cancer in situ and basal cell or squamous cell carcinoma of the skin
- 6. Breast cancer requiring bilateral breast/chest wall radiation therapy.

Notes about eligibility:

- If your site can accommodate consenting and orally administering questionnaires via translator to patients in languages other than English, then non-English speaking patients are eligible.
- Participants enrolled to the FABREC Trial may be enrolled to other treatment and/or non-treatment trials if the consenting investigator deems that there are no contraindications.
- Concurrent systemic therapy will be considered on a case-by-case basis. Please ask the study co-chairs about whether any systemic therapy may be administered concurrently with PMRT.
- A pregnancy test is not required per FABREC protocol.
- Microscopically positive surgical margins are permitted.
- Patients should only be enrolled in this study if the treating physician feels it is medically appropriate for the patient to receive the radiation therapy outlined in this protocol.
- Reconstruction will be considered immediate if it occurred:
 - At the time of mastectomy
 - OR**
 - Up to one month after mastectomy and before radiation treatment planning
- Patients who have stage 0 disease (ductal carcinoma in situ) may undergo radiation therapy after mastectomy to reduce the risk of recurrence, especially in the setting of positive/close margins and/or extensive involvement of the breast. As our purpose is to evaluate patient outcomes after mastectomy and immediate reconstruction, we seek to include patients with stage 0 disease who are receiving radiation in this setting.

3.3 Inclusion of Women and Minorities

Women of any race/ethnicity are eligible for this trial. Women who are pregnant or nursing are excluded from this trial.

4. PRETREATMENT EVALUATIONS/MANAGEMENT

It is necessary to delay enrollment until after mastectomy and reconstruction because a large percentage of patients will not meet the criteria for radiation therapy (and, therefore, for the study) once the pathology results from the mastectomy become available.

5. REGISTRATION AND RANDOMIZATION PROCEDURES

5.1 Registration Process for all sites

This section applies to DF/HCC Institutions (Dana-Farber/Harvard Cancer Center) and all other investigative sites.

To register a participant on the FABREC Trial, please follow these steps:

- Each participating site should identify eligible participants at their site.
- The consenting investigator should approach the patient and hold an informed consent discussion.

- If the potential participant agrees to participate, the consenting investigator and the patient should both sign the Informed Consent document.
- The study staff should then send the following documents to the Central Study Coordinator (CSC) via secure email to [contact] or via fax to [contact] (be sure to write ATTENTION: FABREC Central Study Coordinator on your fax cover sheet).
 1. Signed Informed Consent Form (all pages)
 2. Signed HIPAA authorization form (if applicable: At some sites the HIPAA authorization form and the informed consent document are two separate documents. At other sites, the HIPAA authorization form is contained within the informed consent document, so only the informed consent document need be submitted)
 3. Completed Eligibility Checklist
- The CSC will review the eligibility checklist to ensure that all fields are complete and that all values are within the acceptable range allowed by the protocol. If any information is missing, the CSC will contact the site.
- Next the CSC will work with the Dana-Farber Office of Data Quality (ODQ) to register and randomize the participant.
- Within 24 business hours*, the CSC will email the following information to the site:
 1. Confirmation that the participant has been successfully registered
 2. The participant's unique study ID number
 3. The arm to which the participant was randomized

*Business hours for this study are defined as: Monday through Friday from 8:00 AM to 5:00 PM Eastern Time, not including holidays.

If you need expedited assistance during normal business hours (Eastern Standard Time), please contact the FABREC Central Study Coordinator at [contact] or [contact].

5.2 Study Enrollment Timing

REGISTRATION: Participant must be registered and randomized before protocol treatment (PMRT) begins.

BASELINE PATIENT QUESTIONNAIRE: The baseline questionnaire can be administered to the patient immediately following signed consent (**recommended**). The baseline questionnaire must be completed by the participant after she signs informed consent but before PMRT begins.

[figure not shown]
TREATMENT: Protocol treatment (PMRT) must begin ≤ 4 -months after randomization. Issues that would cause treatment delays should be discussed with the Study Chairs. Permission to deviate from DF/HCC SOP REGIST-101A has been approved and is documented in OnCore.

The rationale for allowing ≤ 4 months between randomization and start of PMRT is that there are a lot of treatment-related activities that must occur between Arm Assignment and PMRT

Initiation including: chemotherapy must be completed (as/if applicable); sequential inflations of the tissue expander need to be completed (as/if applicable); simulation must be performed locally at the treating site; the physics plan must be generated and approved locally at the treating site; and treatment verification films need to be approved locally at the treating site.

Note: the sponsor does not need to pre-approve your PMRT plan.

Information about PMRT treatment planning will be collected via Medical Record Review CRFs. The PMRT Treatment Plan for a patient does **not** need to be submitted prior to initiation of PMRT; this will reduce study burden on sites and clinicians.

Note: Concurrent systemic therapy will be considered on a case-by-case basis. Please ask the study co-chairs about whether any systemic therapy may be administered concurrently with PMRT.

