8. SCHEDULE OF ASSESSMENTS

	Prior to Enrollment (Screening)	Baseline (After participant signs informed consent)	During Radiation Therapy (both arms)	30 Days after RT completion	6 mos. +/- 4 weeks after RT initiation	12 mos. +/- 4 weeks after RT initiation	18 mos. +/- 4 weeks after RT initiation	Every year for 10 years after RT initiation
Medical chart review	X	X		X		X		X
SAE Reporting			Reportable SAEs that occur at any time between initiation of PMRT and 3-years after the initiation of PMRT must be submitted via InForm (see AE section).					
Radiation Treatment Information				X				
Photo Evaluation		X			X	X	X	
Participant Questionnaires		X			X	X	X	
Annual Follow-Up								X

Medical Chart Review. Medical Record Review CRFs will collect data on sociodemographic information, social history, cancer diagnoses, co-morbidities, treatment details, radiation treatment, surgical history and follow up, toxicities, medical history and follow up, disease recurrence, significant clinical events, and mortality.

Study Visits. Because this is a pragmatic trial, there are no protocol mandated study visits. All clinic visits are per standard of care.

Solicited AEs and Expedited SAE Reporting. See Adverse Event Reporting section of protocol for full details.

Radiation Treatment Information. Sites will enter specific information related to the radiation treatment received. This information will be collected by reviewing participants' medical charts at the end of treatment.

Photo evaluation. In order to assess reconstruction, de-identified photos of participant reconstruction will be submitted for evaluation by the Study Chairs or delegate. The participant may take and submit the reconstruction photographs herself (see appendix for patient-facing instructions on how to take and submit reconstruction photographs), or any clinician (nurse, doctor, etc.) who has been trained on the FABREC protocol may take reconstruction photographs.

In extremely rare cases where submission of photographs is not possible, the study chairs will work with the site investigator to complete the Cosmetic Outcome CRFs.

Participant Questionnaires. The following contain items from the following instruments:

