8.1 Administration of Patient Questionnaires

Each participant can choose to complete each questionnaire in writing or orally. Each participant can choose to return his/her questionnaire responses in-person, via postal mail, by phone, scanning and emailing, faxing, or texting (participants may text photographs of the completed questionnaire pages).

The enrolling site staff will be responsible for administering the Baseline Questionnaire to the participant. The Baseline Questionnaire must be administered after the participant has signed informed consent but before protocol treatment begins. It is operationally easiest to administer the Baseline Questionnaire immediately after the participant signs informed consent.

The Central Study Coordinator will administer the Follow-up Questionnaires to participants. In the consent form that patients sign, it is clearly stated that the patient's contact information will be shared with the Central Study Coordinator who sits at Dana-Farber Cancer Institute in Boston, MA for the purposes of questionnaire administration and gift card distribution. A participant will be contacted by the Central Study Coordinator up to five times per timepoint in an attempt to complete each patient study questionnaire. The CSC may contact the participant via email, text message (texts will only be used if participant explicitly responds on their baseline questionnaire that we may contact them via text message), in-person, phone, or postal mail, as appropriate. The participant may return their survey via email, in-person, phone, orally, written, fax, or text message, based on patient preference. If a participant does not respond after five attempts, then the Central Study Coordinator will ask the enrolling site's staff to attempt contact before the survey deadline. If the enrolling site's staff is unable to make contact after three attempts, then the questionnaire will be marked as missing and the participant will not be contacted regarding that questionnaire again.

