To determine the primary endpoint among those measurement scales, we surveyed patients who had undergone radiation therapy after mastectomy and immediate reconstruction and found that the majority of chose **the Physical Well-Being (PWB) subscale of the FACT-B (version 4) to be the most important element of their quality of life, regardless of age** (data not shown, manuscript in preparation). Based on this result, we selected the FACT-B PWB score as the primary endpoint of this study. To adjust for QoL at baseline, we will compare change in PWB score (relative to each patient's pre-radiation score) between the short and long-course treatment groups, instead of comparing PWB scores between the two groups.

Statistical analysis of the primary endpoint and power: As per the intention-to treat principle, the primary analysis population will be all women who are randomly assigned to receive either short-course or long-course (conventional) radiation therapy. The secondary analysis population will be the per-protocol cohort. We hypothesize that the short-course radiation therapy will lead to improved PWB scores compared to the conventional long-course treatment. To confirm this hypothesis, we will use Analysis of Covariance (ANCOVA) models. **Change in the FACT-B PWB subscale (7 items) score at 6 months relative to baseline** will be the response variable, and the intervention group indicator (long-course versus short-course radiation therapy) and age group (below 45 vs. 45 or above) will be included in the ANCOVA model as independent variables. Using change in the PWB score relative to baseline will give us a more normal distribution of outcomes, versus using the score itself. **The age threshold of 45 years was selected by our patient advocates.**

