In addition to age stratification (see 10a and 10b), heterogeneity or variation in outcomes will be examined based on pre-specified patient, cancer and treatment-related attributes (“**Table: Pre-specified attributes to examine heterogeneity/patient subgroups**”). These factors are included because they may have an independent association with the outcomes examined. As shown in the power considerations for Objective 1, with our sample size we will have a sufficient power to detect heterogeneity of treatment effect. We will not adjust for the multiplicity of the statistical testing, because the goal of the HTE analyses is not to confirm a specific treatment heterogeneity hypothesis, but to generate hypotheses of potential treatment

heterogeneity. Towards this end, we will focus more on describing the estimated treatment differences in each of pre-specified subgroups than testing.

We have also planned analyses to identify subgroups of patients in which the treatment effect (benefit of short-course therapy) is potentially more pronounced than the average treatment effect, using a multivariable scoring approach.⁵⁵ Specifically, we will derive a multivariable model that predicts the treatment difference for each patient. Based on the predicted treatment difference scores, we will be able to define subgroups or clusters of patients who benefit more from short-course radiation therapy than the average patient on the study. For example, we will make two subgroups: one which consists of patients only with positive predicted treatment differences, and the other which consists of the remaining patients with negative predicted treatment difference. We will estimate the average treatment difference in each of the two subgroups and also perform a test for interaction.

Table: Pre-specified attributes to examine heterogeneity/patient subgroups	
Patient attributes:	Age (younger than 45, 45 and above) Smoking status Body mass index Comorbidity (hypertension, diabetes) Mastectomy specimen weight
Cancer attributes:	Tumor type (ductal, lobular, mixed histology) Tumor size Receptor status Tumor grade
Treatment attributes:	Number of nodes removed Expander versus permanent implant Volume of implant/expander fill Chemotherapy (yes/no) and regimen and timing of chemo Hormonal therapy Radiation therapy fields Bolus regimen Use of acellular dermal matrix Mastectomy scar location Use of biologic therapy

10f. AE Monitoring

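### The baseline PWB score may be taken while chemotherapy or expander inflation is unfinished; the arm comparison stays unbiased, but the primary model leaves avoidable variance in the change score

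*Combined protocol and SAP*

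**What the plan says.** All references are to the combined protocol and SAP.

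- **Baseline timing.** Section 5.2: "The baseline questionnaire can be administered to the patient immediately following signed consent", marked as recommended. The outer limit is wider: "The baseline questionnaire must be completed by the participant after she signs informed consent but before PMRT begins". Section 8.1 repeats the preference: "It is operationally easiest to administer the Baseline Questionnaire immediately after the participant signs informed consent".
- **Gap before radiation.** Section 5.2 allows up to 4 months from randomization to PMRT. Its reasons include that "chemotherapy must be completed (as/if applicable); sequential inflations of the tissue expander need to be completed (as/if applicable"), alongside simulation, planning and verification.
- **Primary time point.** Section 8 sets it at "6 mos. +/- 4 weeks after RT initiation". It is counted from radiation, not from the baseline questionnaire.
- **Primary analysis.** Section 10b: "To adjust for QoL at baseline, we will compare change in PWB score". It describes the baseline as a pre-radiation score, and the ANCOVA it specifies has two terms, arm and age group. Section 5.3 stratifies by center and age.
- **Chemotherapy in the analysis.** Section 10e lists "Chemotherapy (yes/no) and regimen and timing of chemo" among the heterogeneity attributes. Section 10c says chemotherapy regimen will be checked for balance, but under clinical outcomes.

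No section asks for a second PWB score close to the start of radiation or a minimum time since chemotherapy.

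**The concern.** A baseline taken at consent precedes radiation but need not follow chemotherapy or expansion. One woman may answer during chemotherapy, another before it starts, a third well after it ended, and a fourth may never have it. Their changes in PWB to 6 months then differ for reasons unrelated to the radiation schedule, and the primary model has no term to absorb this.

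Three things are at stake:

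- the residual variance of the primary outcome;
- the baseline-to-6-month correlation of 0.65 to 0.70 on which section 10b relies;
- the meaning of the mean change within one arm.

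The shift may go either way. A baseline during chemotherapy leaves room for recovery, whereas one before chemotherapy may be followed by worsening.

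**Working it through.** **1. The interval.** At most 4 months from randomization to PMRT plus 6 months gives 10 months, or about 11 with the 4-week window. This is an outer limit. Under Appendix B, women without postoperative chemotherapy must start radiation within 4 months of mastectomy, and enrollment follows mastectomy (section 4), so their gap is shorter.

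**2. The plan's own figures.** Inputs from sections 10b and 5.3: 200 per arm, difference 2.8, two-sided 0.05, SD of change 4.0, 40% younger women, interaction contrast 4.0 − 2.0 = 2.0.

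- Main power is above 0.999. This agrees with the table's >0.99 but not with the 93% in the text.
- Interaction SE = SD × √(2/80 + 2/120) = SD × 0.204. Power at SD 3.5, 4.0 and 4.5 is 0.80, 0.69 and 0.59, as in the table.
- SD of change = 6√(2(1−ρ)) = 5.02 at ρ = 0.65 and 4.65 at ρ = 0.70. The stated 4.2 and 3.6 equal 6 × 2(1−ρ), without the square root. Results below are therefore given on both 4.0 and 5.02.

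**3. Added variance.** Assume a share p of women has an extra mean shift of d points, the same in both arms. Then SD² = SD₀² + p(1−p)d², and information lost = 1 − SD₀²/SD². The documents give neither p nor d. Power for 2.0 uses 190 per arm (5% dropout); interaction power uses 200, as in the plan.

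| SD₀ | p | d | SD | Information lost | Power, 2.0 points | Interaction power |
|---|---|---|---|---|---|---|
| 4.0 | none | none | 4.00 | 0 | 0.998 | 0.69 |
| 4.0 | 0.2 | 3 | 4.18 | 8% | 0.997 | 0.65 |
| 4.0 | 0.3 | 3 | 4.23 | 11% | 0.996 | 0.64 |
| 4.0 | 0.3 | 5 | 4.61 | 25% | 0.988 | 0.57 |
| 4.0 | 0.5 | 5 | 4.72 | 28% | 0.985 | 0.55 |
| 5.02 | none | none | 5.02 | 0 | 0.973 | 0.50 |
| 5.02 | 0.5 | 5 | 5.61 | 20% | 0.93 | 0.42 |

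Power for 2.8 points is at least 0.998 in every row.

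**4. Weaker correlation.** With SD 6, 190 per arm and the change-score model, ρ = 0.50 gives SD 6.00 and power 0.995 (2.8 points) or 0.90 (2.0). ρ = 0.30 gives SD 7.10 and power 0.97 or 0.78. Adding baseline PWB makes the residual SD 6√(1−ρ²). At ρ = 0.30 that is 5.72, with power 0.998 or 0.93.

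**5. Bias.** A simulation (4,000 runs, 190 per arm, SD₀ 5.02) gave 30% to 50% of women a mean recovery of 3 to 5 points with SD 3 to 4, equally in both arms. The control-arm mean change moved by +1.5 to +2.5 points with no radiation effect. The between-arm estimate stayed at 2.79 to 2.82 for a true 2.8, type I error was 0.045 to 0.053, the SD rose to 5.6 to 6.3, and power was 0.989 to 0.998.

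**6. Chance imbalance.** The between-arm difference in the affected share has SD √(2p(1−p)/200), which is 0.05 at p = 0.5. With d = 5 it moves the estimate by 0.25 points (one SD). This is the variance of step 3 seen in a single trial, not an extra loss.

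**7. What a covariate can recover.** It removes p(1−p)d², but not variation in the shift among women of the same status. In the simulated case with share 0.5, mean 5 and SD 4, the extra variance is 6.25 + 0.5 × 16 = 14.25, of which the covariate removes 6.25.

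**The case against.** The strongest reply is that the primary result is a randomized contrast. The timing rule is the same in both arms, so the nuisance change cancels in expectation. This stands. A reader might infer that the treatment effect is confounded by recovery from chemotherapy. The documents do not support that: section 10b compares change between randomized arms, and no section plans to read within-arm change as the radiation effect.

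The size is also an assumption. Both treatments apply only to some women, the share is not given, and the plan's SD may already include part of this variation. This stands too, so the 8% to 28% is illustrative. Power for 2.8 points is not in danger.

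A reader might also infer that randomization should wait until chemotherapy and inflation are finished. The documents do not support that as a correction. Section 5.2 gives a deliberate rationale for the window, in a pragmatic trial without mandated visits, and delay would cost planning time and some consented women. The recommended consent-time baseline already precedes arm assignment under section 5.1, an advantage in an open-label trial with a self-reported outcome.

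What remains is that chemotherapy status can be known at randomization, plausibly predicts the change, and is absent from the primary model.

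**Conclusion.** The point holds as a matter of precision and interpretation, not of bias. For an unknown share of women the primary change score includes change from chemotherapy or expander inflation. The between-arm estimate remains unbiased with correct type I error, and power for 2.8 points stays at about 0.97 or higher even if ρ falls to 0.30.

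The avoidable loss is 8% to 28% of information on the plan's SD of 4.0, or up to 20% on the re-derived 5.02, assuming p of 0.2 to 0.5 and d of 3 to 5. It is felt mainly at a 2-point difference and in the age interaction, where power of 0.69 would fall to between 0.65 and 0.55. Section 10e's statement that power for heterogeneity is sufficient has little room for that. Within-arm change could move by a couple of points with no radiation effect, which is about the 2-point change that section 10b cites as clinically meaningful.

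**What to change.** 1. Keep the baseline questionnaire at consent.
2. Add to the primary ANCOVA baseline PWB and a pre-specified four-level covariate for chemotherapy status, fixed at randomization: none given or planned before PMRT; completed; ongoing; planned but not yet started. The last two must stay separate because their shifts may have opposite signs.
3. Optionally add expander inflation status at randomization: complete, not complete, not applicable.
4. Do not adjust for the interval from baseline to radiation. It is determined after randomization.
5. State in section 10b that within-arm change is not interpreted as the effect of radiation.

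The cost is SAP wording, a few degrees of freedom out of about 380 analyzed women, and one item recorded at registration or derived from the treatment details that section 8 already abstracts. No patient's care or schedule changes. One limit: status at randomization describes the baseline well only when the questionnaire is completed at consent as recommended, and less well for women who complete it later in the permitted window.
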